**Table 10-1: Laboratory measurements**

Category	Panel	Variable
Hematology	Red blood cell	RBC count, hemoglobin, hematocrit
	White blood cell	WBC count

**Table 10–1: Laboratory measurements**

Category	Panel	Variable
	White blood cell differential	Absolute counts: ANC, basophils, eosinophils, ALC, monocytes Percentages: neutrophils/leukocytes, basophils/leukocytes, eosinophils/leukocytes, lymphocytes/leukocytes, monocytes/leukocytes
	Platelet	Platelet count
Chemistry	Liver function	ALP, ALT, AST, GGT, total bilirubin a , LDH
	Enzymes	Creatine kinase, amylase
	Proteins	Total protein, albumin, alpha- and beta- globulins, hsCRP
	Kidney Function	Urea- nitrogen, creatinine
	Lipids	Triglycerides, total cholesterol, LDL cholesterol, HDL cholesterol,
	Electrolytes	Calcium, phosphate, sodium, potassium, chloride, and magnesium
	Hormones	Procalcitonin
Urinalysis b	Dipstick	pH, nitrite, protein, glucose, ketones, urobilinogen, bilirubin, blood,
	Urine Sediment	Leukocytes
	Quantitative	Albumin, creatinine, protein

ALC=absolute lymphocyte count; ALP=alkaline phosphatase; ALT=alanine aminotransferase; ANC=absolute neutrophil count; AST=aspartate aminotransferase; GGT=gamma-glutamyltransferase; HDL=high density lipoprotein; hsCRP=high sensitivity C-Reactive Protein; LDH=lactate dehydrogenase; LDL=low density lipoprotein; RBC=red blood cell; WBC=white blood cell

a Direct bilirubin will also be measured when total bilirubin is elevated.

b Urine microscopy will be performed if urine is positive for protein, blood, nitrite, or leukocytes.

### 10.3.1 Potential drug-induced liver injury

A separate table will present participants who meet one or more of the following potential drug-induced liver injury (PDILI) criteria at any visit:

- Aspartate aminotransferase (AST): >3 x ULN, >5 x ULN, >10 x ULN, >20 x ULN
- Alanine aminotransferase (ALT): >3 x ULN, >5 x ULN, >10 x ULN, >20 x ULN
- AST or ALT: >3 x ULN, >5 x ULN, >10 x ULN, >20 x ULN
- Total bilirubin (TBL): >1.5 x ULN, >2 x ULN
- Alkaline phosphatase (ALP) >1.5 x ULN
- Alanine aminotransferase (ALT) or Aspartate aminotransferase (AST)  $\geq$ 5x Upper limit of normal (ULN)
- (ALT or AST increase  $\geq$ 3x ULN) and Total bilirubin  $\geq$ 2x ULN
- AST or ALT  $\geq$  3 x ULN

- AST or ALT  $>3 \times$  ULN, with TBL  $\geq 1.5 \times$  ULN
- AST or ALT  $>3 \times$  ULN, with TBL  $\geq 2 \times$  ULN
- (ALT or AST increase  $>3 \times$  ULN) and Total bilirubin  $>2 \times$  ULN and ALP  $<2 \times$  ULN (Hy's Law)
- (ALT or AST  $\geq 3 \times$  ULN) and (eCRF question for "Is the subject exhibiting symptoms of hypersensitivity" = Yes or eCRF question for "Is the subject exhibiting symptoms of Hepatitis" = Yes at the same date +/- 2 days)
- (ALT or AST)  $\geq 3 \times$  ULN (and  $\geq 2 \times$  Baseline) and  $<5 \times$  ULN and Total bilirubin  $<2 \times$  ULN and (eCRF question for "Is the subject exhibiting symptoms of hypersensitivity" = No and eCRF question for "Is the subject exhibiting symptoms of Hepatitis" = No at the same date +/- 2 days)
- (ALT or AST)  $\geq 5 \times$  ULN (and  $\geq 2 \times$  Baseline) and Total bilirubin  $<2 \times$  ULN (eCRF question for "Is the subject exhibiting symptoms of hypersensitivity" = No and eCRF question for "Is the subject exhibiting symptoms of Hepatitis" = No at the same date +/- 2 days)

The laboratory results listing will flag participants who are experiencing PDILI including Hy's Law.

## **10.4 Vital signs, physical findings, and other observations related to safety**

### **10.4.1 Vital signs**

The following vital signs measurements will be obtained:

- Pulse rate
- Systolic and diastolic blood pressure
- Body weight
- Temperature (oral preferred, ear or axillary permitted)

A by-participant listing of all vital sign measurements and change from Baseline will be presented by treatment group and timepoint. The listing will include a flag for measurements identified as markedly abnormal (MA) as calculated by the criteria outlined in [Table 10–2](#).

Descriptive statistics will be reported for all vital sign measurements. Measured values and changes from Baseline will be summarized by vital signs variables, timepoint and treatment group.

Summarization will be as treated, participants who missed treatments will not be summarized.

**Table 10–2: MA Criteria for Vital Signs**

Variable	Unit	Low	High
Systolic blood pressure a	mmHg	$\leq 90$ and a decrease from Baseline of $\geq 20$	$\geq 180$ and an increase from Baseline of $\geq 20$
Diastolic blood pressure a	mmHg	$<50$ and a decrease from Baseline of $\geq 15$	$>105$ and an increase from Baseline of $\geq 15$
Pulse rate a	bpm	$<50$ and a decrease from Baseline of $\geq 15$	$>120$ and an increase from Baseline of $\geq 15$

**Table 10–2: MA Criteria for Vital Signs**

Variable	Unit	Low	High
Temperature	°C		>101.0°F (38.3°C)
Body Weight	1	≥ 10% decrease from Baseline	≥ 10% increase from Baseline

Repeated and unscheduled measurements will be handled as described in Section 4.2.8.

#### 10.4.2      **Electrocardiograms**

Standard 12-lead ECG recordings will be taken in triplicate with the participant resting in the supine position for at least 15 minutes and before obtaining any blood samples for assessments of laboratory variables. The following variables will be reported:

- Heart rate
- RR interval
- PQ/PR interval
- QRS duration
- QT interval
- QT corrected for heart rate using Fridericia's formula ( $QTcF = QT/(RR^{1/3})$ )

The individual measurements and the mean of the triplicate measurements will be reported in the by-participant listings. The listing will also include the change from Baseline (based on the mean of the triplicate measurements at each timepoint) and will be presented by treatment group and timepoint. The listing will also include a flag for values identified as MA/PCS as defined by the following criteria.

**Table 10–3: MA/PCS criteria for Electrocardiograms**

Parameter	Abnormality Criteria
QT interval (ms)	>=500ms
	>=60ms increase from Baseline
QTc(F) (ms)	>=500ms
	>=60ms increase from Baseline
PR interval (ms)	Treatment-emergent value >200ms
QRS interval (ms)	Treatment-emergent value >100ms
Heart rate (bpm)	<50bpm
	>120bpm

Measured values and changes from Baseline will be summarized by treatment group at each timepoint and by ECG variable (based on the mean of the triplicate values at each timepoint).

Summarization will be as treated, participants who missed treatments will not be summarized.

The following cut-points in QTcF (raw data and change from Baseline) will be summarized categorically by treatment group (number and percentage of participants) and visit/timepoint. The denominator for the percentages will be the number of participants with a non-missing measurement for the variable at the specific visit/timepoint.

Raw QTcF data:

- <450msec
- $\geq$ 450msec to <480msec
- $\geq$ 480msec to <500msec
- $\geq$ 500msec

Change from Baseline QTcF:

- <30msec
- $\geq$ 30ms to <60msec
- $\geq$ 60msec

Electrocardiogram findings for the individual triplicate measurements will be listed separately.

Repeated and unscheduled measurements will be handled as described in Section 4.2.8.

In the event that the complete set of triplicate measurements is not available at a specified timepoint the data will be handled as described in Section 4.2.6.

#### **10.4.3      Suicidality**

A full Columbia Suicide Severity Rating Scale (C-SSRS) assessment will be performed only when participant has a positive response to the suicidal ideation query. Results of suicidal ideation and C-SSRS will be listed by treatment group, participant and time point.

#### **10.4.4      Other safety variables**

Results of Serum and Urine pregnancy test will be listed.

Results of tuberculosis signs and symptoms questionnaire will be listed.

Results of Chest X-Ray will be listed.

Results of interferon-gamma release assay (IGRA) tuberculosis test will be listed.

Physical and neurological examination findings will be listed.

Results of serology testing for human immunodeficiency virus (HIV), Hepatitis B and Hepatitis C will be listed.

Participants experiencing severe headache will complete the Headache Questionnaire daily until resolution (ie, if headache becomes moderate or mild, normal collection of AEs should apply). At the clinic visit when the severe headache is reported, the Headache Questionnaire will be followed by a neurological assessment (including fundoscopy). If the severe headache is initially reported at a home visit or during a telephone call, the participant should be reviewed at the study site as soon as is practically possible for further investigations. Further workup will be performed at the discretion of the investigator and may include, eg, a computed tomography scan, magnetic resonance imaging and/or a lumbar puncture for cerebral spinal fluid collection. In addition, samples for exploratory biomarkers should be taken for participants experiencing severe headache (Table 5-2 of the protocol). These investigations will be performed to further understand the mechanism of headache in these participants.

The results of the headache questionnaire, neurological examination and any additional tests performed (CT scan, fundoscopy and LP for CSF collection) will be listed for each

participant having experienced severe headache. No summary tabulations will be provided for these assessments

Stool collection and analysis will be performed for participants reporting moderate or severe diarrhea. Results of the analysis will be listed for each participant. No summary tabulation will be provided for this assessment.

## 11 OTHER ANALYSES

Exploratory pharmacogenetics variables samples date/timepoint collection will be listed.

Exploratory RNA, proteins, and metabolites variables samples date collection will be listed.

For the presentation of the data for the interim analyses, each participant will be presented separately in the form of a patient profile which will include the following information:

- Participant demographics (age, gender, race, BMI, body weight at Screening)
- Treatment group
- Medical history (including procedure history)
- Prior and concomitant medication
- Drug administration (including whether performed at site or at home)
- AEs
- Safety laboratory variables (individual figures over time by panel [hematology, clinical chemistry, coagulation] and variable)
- Vital signs variables (individual figures over time by variable)
- ECG variables (individual figures over time by variable)
- IgG (individual figures over time for observed values and changes from Baseline)

## 13 APPENDICES

### 13.1 Conversion of iRODS scores

Table 13-1: Nomogram

R-ODS summed raw score	Rasch person location	centile metric	Corresponding SE
	(logits)		$SE = 0.4248 - 0.0016 * \text{location} + 0.0140 * \text{location}^2$
0	-6.95	0	1.11
1	-6.03	6	0.94
2	-5.36	11	0.84
3	-4.87	14	0.76
4	-4.48	16	0.71
5	-4.14	19	0.67
6	-3.84	21	0.64
7	-3.57	22	0.61
8	-3.32	24	0.58
9	-3.09	26	0.56
10	-2.87	27	0.54
11	-2.66	28	0.53
12	-2.46	30	0.51
13	-2.26	31	0.5
14	-2.07	32	0.49
15	-1.88	34	0.48
16	-1.70	35	0.47
17	1.52	36	0.46
18	1.33	37	0.45
19	-1.15	39	0.45
20	0.97	40	0.44
21	-0.79	41	0.43
22	-0.61	42	0.43
23	-0.42	43	0.43
24	-0.24	45	0.43
25	-0.05	46	0.42
26	0.14	47	0.42
27	0.34	48	0.43
28	0.53	50	0.43
29	0.73	51	0.43
30	0.94	52	0.44
31	1.15	54	0.44
32	1.36	55	0.45
33	1.58	57	0.46

R-ODS summed raw score	Rasch person location	centile metric	Corresponding SE
	(logits)		$SE = 0.4248 - 0.0016 * \text{location} + 0.0140 * \text{location}^2$
34	1.81	58	0.47
35	2.04	60	0.48
36	2.28	61	0.49
37	2.54	63	0.51
38	2.80	65	0.53
39	3.09	67	0.55
40	3.40	69	0.58
41	3.74	71	0.61
42	4.11	73	0.65
43	4.54	76	0.71
44	5.03	80	0.77
45	5.59	83	0.85
46	6.25	88	0.96
47	7.07	93	1.11
48	8.11	100	1.33

This document cannot be used to support any marketing authorization application and any extensions or variations thereof.  
PUBLIC COPY

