### **8.1.1 Derivations of primary efficacy variable**

The iRODS is a linearly weighted patient-reported outcome measure (questionnaire) that specifically captures activity and social participation limitations in patients with CIDP. The iRODS scale was constructed based on the World Health Organization (WHO) International Classification of Functioning, Disability and Health, literature search, and patient interviews.

All 24 items of iRODS meet Rasch model expectations. The questionnaire consists of 24 items (including eating, taking a shower, walking a flight of stairs, standing for hours, etc.) and assesses a patient's perception of their ability to perform daily and social activities. Patients have 3 response options: 0=impossible to perform; 1=performed with difficulty; and 2=easily performed, performed without difficulty.

The raw sum scores of iRODS (range 0 to 48) is an ordinal scale and does not allow for easy interpretation of differences. For this reason, the ordinal scale will be translated to log odds units (logits) scale using the nomogram in Section 13.1, placing patients' estimates on the same logit scale. The primary analysis and iRODS summary will be performed on logit locations. For easier interpretation the person locations (logits) will be translated to centile metric scores changing from 0 (most severe activity and social participation restrictions) to 100 (no activity and social participation limitations). Both transformed and untransformed data will be provided in tables and key results will be presented in transformed and original units to aid interpretation based on the raw scores.

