### **8.1.2 Analysis of the primary efficacy variable**

The primary analysis will be based on a MMRM analysis (fixed effect terms: treatment group, the Baseline location iRODS score, route of administration of prior Ig therapy (as captured in the eCRF Prior and Concomitant Medication form), assessment week (at pre-specified levels determined by the visit schedule) and the treatment by week interaction and study participant as a random effect, and utilize an unstructured covariance matrix).

The Kenward-Roger approximation will be used to estimate denominator degrees of freedom. In case of non-convergence, the model will be fitted using the following covariance matrices until convergence is met: Heterogeneous Toeplitz, Heterogeneous autoregressive, Toeplitz, Autoregressive.

SAS proc MIXED will be used:

- a. Subject ID, treatment group, prior Ig therapy and visit will be set as classes

---

- b. The model will be specified with covariates baseline score, treatment group, prior Ig therapy, visit and treatment\*visit
- c. The repetition variable is visit.
- d. Subject ID is set as random factor.
- e. Covariance structure as described above.
- f. LS means, differences and confidence limits for treatment\*visit are requested.

An estimate for the placebo-adjusted treatment effect with 90% CI will be produced on logit location scale, on the raw scores as well as centile metric scores.

Imputation rules are given in Section 4.2.1.

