## 8.2 Statistical analysis of the other efficacy variables

### 8.2.1 CIDP relapse, MMRM and summary tables will be performed on the FAS and repeated for the PPS for iRODS, adjusted INCAT and clinician reported grip strength.CIDP relapse (iRODS)

CIDP relapse (iRODS) is defined as a clinically important deterioration from Baseline in iRODS score, i.e. a standardized change from baseline smaller than or equal to the minimum clinically important differences-standard error (MCID-SE) of  $\leq -1.96$ .

This standardized change from baseline refers to individual person-level responsiveness calculated by individual change divided by their corresponding SE of difference at a given timepoint. [Va15]

$$\text{"MCID - SE"} = \frac{\text{Standardized value}_{\text{Visit}} - \text{Standardized value}_{\text{Baseline}}}{\sqrt{\text{SE}_{\text{Visit}}^2 + \text{SE}_{\text{Baseline}}^2}}$$

Values and changes from Baseline in iRODS scores will be summarized by treatment group and for all participants and listed by treatment group at each scheduled assessment during the Treatment and Observation Period.

The point estimate and the corresponding 2-sided 90% CI for the difference between placebo and rozimab CIDP relapse rates up to week 13 will be reported. The CI will be constructed using the asymptotic standard error (asymptotic Wald confidence limits).

Analyses will be performed for the FAS utilizing the observed cases.

Sensitivity analysis for relapse will be performed in the same way, however for the PPS.

The rule for handling missing data is described in Section 4.2.1.

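### SAP Table 13-1: the logits for raw iRODS scores 17, 18 and 20 appear without a minus sign in the text supplied and contradict the rest of the table

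*SAP*

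**What the plan says.** SAP 8.1.1 states that "the ordinal scale will be translated to log odds units (logits) scale using the nomogram in Section 13.1", and that "The primary analysis and iRODS summary will be performed on logit locations". SAP 8.1.2 takes the Baseline logit location as a covariate in the MMRM and asks for the treatment effect with its 90% CI, which "will be produced on logit location scale, on the raw scores as well as centile metric scores".

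SAP 8.2.1 defines iRODS relapse by a standardized change, the MCID-SE, with cut-off -1.96 or lower. It describes this as "individual person-level responsiveness calculated by individual change divided by their corresponding SE of difference at a given timepoint". Table 13-1 supplies the SE for each score.

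The three rows at issue in Table 13-1 (SAP 13.1), in the order raw score, logit, centile, SE, are:

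- "17 1.52 36 0.46"
- "18 1.33 37 0.45"
- "20 0.97 40 0.44"

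The neighbouring logits are -1.70 (raw 16), -1.15 (raw 19) and -0.79 (raw 21).

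**The concern.** A Rasch conversion table must rise with the raw score. Read as supplied, this one jumps up by 3.22 logits from 16 to 17, falls at 17 to 18 and 18 to 19, jumps up by 2.12 from 19 to 20, and falls again at 20 to 21.

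This single table feeds the primary change score, the Baseline covariate and the iRODS relapse statistic. If the positive values were programmed, a change would be wrong whenever exactly one of Baseline and visit is 17, 18 or 20, or when both are but differ. Patients who worsen into one of these scores could look stable or improved, and patients who start at one could be called relapsed after a trivial change or an improvement.

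The centile output may be exposed as well. SAP 8.1.1 says "For easier interpretation the person locations (logits) will be translated to centile metric scores". If that step is computed from the logit rather than looked up, the centiles inherit the error and only the raw score would reveal it.

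**Working it through.** **Inputs.** All 49 rows of Table 13-1; the SE formula in its header; the MCID-SE formula and cut-off in SAP 8.2.1; 15 subjects per group from SAP 2.4.

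**1. Centile column.** The table gives no centile formula. A linear rescaling between its end rows (-6.95 to 0, 8.11 to 100) is inferred:

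centile = 100 × (logit + 6.95) / (8.11 + 6.95) = 100 × (logit + 6.95) / 15.06

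Rounded, this reproduces the tabulated centile in 46 of 49 rows. The exceptions are raw 17, 18 and 20:

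| Raw | Logit as supplied | Centile from it | Centile with minus sign | Tabulated |
|---|---|---|---|---|
| 17 | 1.52 | 56.2 | 36.1 | 36 |
| 18 | 1.33 | 55.0 | 37.3 | 37 |
| 20 | 0.97 | 52.6 | 39.7 | 40 |

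**2. SE column.** SE = 0.4248 - 0.0016 × location + 0.0140 × location².

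- Raw 17: +1.52 gives 0.4547 and -1.52 gives 0.4596, against 0.46 in the table. Only the negative value rounds correctly.
- Raw 18: 0.4474 or 0.4517, against 0.45. Both signs round correctly.
- Raw 20: 0.4364 or 0.4395, against 0.44. Both signs round correctly.

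The SE column therefore supports the point only at raw 17.

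**3. Minus signs restored.** The logits rise strictly over all 49 rows, and every centile and SE reproduces to rounding (largest differences 0.49 centile and 0.0049 SE).

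**4. Size of the error if the positive values were used.** Each location is too high by twice its absolute value: 3.04, 2.66 and 1.94 logits. Centiles computed from them would be too high by 20.2, 17.7 and 12.9 points.

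**5. Effect on iRODS relapse.** MCID-SE = (visit - Baseline) / √(SE_visit² + SE_Baseline²), with relapse at -1.96 or lower. Two examples with tabulated SEs:

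- 30 to 20, √(0.44² + 0.44²) = 0.622. As supplied, (0.97 - 0.94)/0.622 = +0.05. With the minus sign, (-0.97 - 0.94)/0.622 = -3.07. A relapse is missed.
- 20 to 21, √(0.43² + 0.44²) = 0.615. As supplied, (-0.79 - 0.97)/0.615 = -2.86. With the minus sign, (-0.79 + 0.97)/0.615 = +0.29. A one-point improvement becomes a relapse.

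There are 49 × 48 - 46 × 45 = 282 ordered pairs of different scores that involve 17, 18 or 20. Relapse status differs in 72 of them, and in no other pair:

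- **37 missed.** These are falls to 17 from 24–38, to 18 from 25–37, and to 20 from 27–35. Of 71 true relapses into these scores, the other 34 are still detected.
- **35 false.** Of these, 17 are raw-score improvements.

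The counts are the same with tabulated or formula SEs. Of the 89 pairs that worsen into one of the three scores, 38 would show a logit gain, 5 of them a gain of 2 logits or more.

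**6. Effect on an arm mean.** Suppose one subject among 15 has such a score at Week 13 and an unaffected Baseline. The simple arm mean shifts by 3.04/15 = 0.20, 2.66/15 = 0.18 or 1.94/15 = 0.13 logit. This is not the MMRM estimate. With no such subject the shift is 0.

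**The case against.** The strongest objection is that this may be no error in the plan. The text was read by a program, and a thin minus sign is easily lost. The centiles, and the SE at raw 17, show that the table was built from negative values, which fits a loss at some later step. Against that, 23 of the 26 negative logits (raw 0 to 25) kept their sign in the same text, so a slip on the page itself cannot be excluded. Neither origin can be established from the documents. This objection stands in full as a limit: what is shown is an inconsistency in the supplied text.

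The counts are also conditional. The 72 flips weight all score pairs equally and are 3.1% of all 2,352 ordered pairs of different scores (72/2,352). Neither proportion is a probability in patients. That is right, and the figures should be read only as the size of the error where it occurs.

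There are mitigations:

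- SAP 4.2.1 counts withdrawals, missing Week 13 data and Ig rescue as relapse, so some missed relapses would be counted anyway.
- SAP 8.2.5 adds INCAT, grip strength and investigator-reported relapse to the overall event.
- SAP 8.1.2 and 8.1.2.1 report and list raw, logit and centile scores together, so a large logit jump beside a small raw change could be noticed.
- SAP 8 treats all efficacy as exploratory, without p-values.

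These reduce the consequence. None of them corrects the logit change or removes a false relapse.

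**Conclusion.** The concern holds as an inconsistency in the supplied text of Table 13-1. Exactly three logits (raw 17, 18 and 20) contradict the table's order and its centiles, and minus signs resolve every discrepancy. Whether the original page or the programmed lookup carries the positive values is not known.

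If they were used, the affected locations are wrong by 1.94 to 3.04 logits and iRODS relapse is misclassified in the pairs listed above. The number of subjects concerned cannot be estimated, because the documents give no iRODS distribution.

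Some results are safe in any case. The raw-score analysis is unaffected, as are centiles if they are looked up. The same affected score at both visits still gives a change of 0, and larger falls are still detected as relapses. The linear centile formula is an inference from the end rows, but it reproduces all 46 other rows. Because the logit-scale estimate and its 90% CI are the primary result, the table should be verified before those outputs are relied on.

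**What to change.** 1. Look at the original page of SAP Table 13-1 and at the cells for raw 17, 18 and 20 in the programmed lookup. If both carry minus signs, no correction is needed.
2. Wherever the positive values are found, change them to -1.52, -1.33 and -0.97. If the lookup held them, rerun the logit outputs, any centiles derived from logits, and the iRODS relapse outputs, including the overall relapse event in SAP 8.2.5.
3. Add a programmed check that location rises strictly with raw score and that the centile and SE columns reproduce from location.
4. Optionally, state in SAP 8.1.1 whether centiles are looked up or computed from the logit.

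The cost is one page, three cells and one assertion in the program. SAP edits and reruns arise only if the positive values are found.
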